Appendix F Genetic Research

F 1 Rationale and Objectives

AstraZeneca intends to collect and store DNA for genetic research to explore how genetic variations may affect clinical parameters, risk and prognosis of diseases, and the response to medications. Genetic research may lead to better understanding of diseases, better diagnosis of diseases or other improvements in health care and to the discovery of new diagnostics, treatments, or medications.

In addition, collection of DNA samples from populations with well described clinical characteristics may lead to improvements in the design and interpretation of clinical trials and, possibly, to genetically guided treatment strategies.

F 2 Genetic Research Plan and Procedures

F 2.1 Selection of Genetic Research Population

Study Selection Record

All subjects will be asked to participate in this genetic research. Participation is voluntary and if a subject declines to participate there will be no penalty or loss of benefit. The subject will not be excluded from any aspect of the main study.

Inclusion Criteria

For inclusion in this genetic research, subjects must fulfil all of the inclusion criteria described in the main body of the protocol **and**:

• Provide informed consent for the genetic sampling and analyses.

Exclusion Criteria

Exclusion from this genetic research may be for any of the exclusion criteria specified in the main study or any of the following:

- Previous allogeneic bone marrow transplant.
- Non-leukocyte depleted whole blood transfusion in 120 days of genetic sample collection.

F 2.2 Discontinuation of Subjects from this Genetic Research

Specific reasons for discontinuing a subject from this genetic research are:

• Withdrawal of consent for genetic research: Subjects may withdraw from this genetic research at any time, independent of any decision concerning participation in other

aspects of the main study. Voluntary discontinuation will not prejudice further treatment. Procedures for discontinuation are outlined in Section 4.1.8 of the protocol.

F 2.3 Collection of Samples for Genetic Research

The blood sample for genetic research will be obtained from the subjects at Visit 3 in the treatment period. Although DNA is stable, early sample collection is preferred to avoid introducing bias through excluding subjects who may withdraw due to an AE, such subjects would be important to include in any genetic analysis. If for any reason the sample is not drawn at Visit 3, it may be taken at any visit until the last study visit. Only 1 sample should be collected per subject for genetics during the study. Samples will be collected, labelled, stored, and shipped as detailed in the Laboratory Manual.

F 2.4 Coding and Storage of DNA Samples

The processes adopted for the coding and storage of samples for genetic analysis are important to maintain subject confidentiality. Samples will be stored for a maximum of 15 years, from the date of last subject last visit, after which they will be destroyed. DNA is a finite resource that is used up during analyses. Samples will be stored and used until no further analyses are possible or the maximum storage time has been reached.

An additional second code will be assigned to the blood either before or at the time of DNA extraction replacing the information on the sample tube. Thereafter, the sample will be identifiable by the second, unique number only. This number is used to identify the sample and corresponding data at the AstraZeneca genetics laboratories, or at the designated organization. No personal details identifying the individual will be available to any person (AstraZeneca employee or designated organizations working with the DNA).

The link between the subject enrollment/randomization code and the second number will be maintained and stored in a secure environment, with restricted access at AstraZeneca or designated organizations. The link will be used to identify the relevant DNA samples for analysis, facilitate correlation of genotypic results with clinical data, allow regulatory audit and to trace samples for destruction in the case of withdrawal of consent.

F 2.5 Ethical and Regulatory Requirements

The principles for ethical and regulatory requirements for the study, including this genetics research component, are outlined in Section 7 of the protocol.

F 2.6 Informed Consent

The genetic component of this study is optional and the subject may participate in other components of the main study without participating in the genetic component. To participate in the genetic component of the study the subject must sign and date both the consent form for

the main study and the genetic component of the study. Copies of both signed and dated consent forms must be given to the subject and the original filed at the study center. The principal investigator(s) is responsible for ensuring that consent is given freely and that the subject understands that they may freely discontinue from the genetic aspect of the study at any time.

F 2.7 Subject Data Protection

AstraZeneca will not provide individual genotype results to subjects, any insurance company, any employer, their family members, general physician unless required to do so by law.

Extra precautions are taken to preserve confidentiality and prevent genetic data being linked to the identity of the subject. In exceptional circumstances, however, certain individuals might see both the genetic data and the personal identifiers of a subject. For example, in the case of a medical emergency, a global safety physician or an investigator might know a subject's identity and also have access to his or her genetic data. Also, regulatory authorities may require access to the relevant files, though the subject's medical information and the genetic files would remain physically separate.

F 2.8 Data Management

Any genotype data generated in this study will be stored at a secure system at AstraZeneca and/or designated organizations to analyze the samples.

The results from this genetic research may be reported in a separate report from the Clinical Study Report or published in scientific journals.

AstraZeneca and its designated organizations may share summary results (such as genetic differences from groups of individuals with a disease) from this genetic research with other researchers, such as Hospitals, Academic Organization, or Health Insurance Companies. This can be done by placing the results in scientific databases, where they can be combined with the results of similar studies to learn even more about health and disease. The researchers can only use this information for health-related research purposes. Researchers may see summary results but they will not be able to see individual subject data or any personal identifiers.

Some or all of the clinical datasets from the main study may be merged with the genetic data in a suitable secure environment separate from the clinical database.

F 2.9 Statistical Methods and Determination of Sample Size

The number of subjects that will agree to participate in the genetic research is unknown. It is therefore not possible to establish whether sufficient data will be collected to allow a formal statistical evaluation or whether only descriptive statistics will be generated. A Statistical Analysis Plan for genetic research will be prepared where appropriate.

Appendix G Classification of Topical Corticosteroids

Topical corticosteroids (TCSs) are grouped into 7 classes based on vasoconstriction assays, with Class I TCSs the most potent and Class VII TCSs the least potent (Table G1). If a TCS not included in the table below is desired, the investigator should contact the medical monitor to confirm classification. These groups may vary depending on the formulation and concentration and should be considered approximate. In general, ointments are more potent than creams or lotions. Potency is also increased when TCSs are used under occlusive dressings or in intertriginous areas.

Table G1 Classification of Representative TCSs

Potency	Class	TCS	Formulation	Strength (%)
Very high	I	Augmented betamethasone dipropionate	0	0.05
		Clobetasol propionate	C, F, or O	0.05
		Diflorasone diacetate	0	0.05
		Halobetasol propionate	C or O	0.05
High	П	Amcinonide	C, L, or O	0.1
		Augmented betamethasone dipropionate	С	0.05
		Betamethasone dipropionate	C, F, O, or S	0.05
		Desoximetasone	C or O	0.25
		Desoximetasone	G	0.05
		Diflorasone diacetate	С	0.05
		Fluocinonide	C, G, O, or S	0.05
		Halcinonide	C or O	0.1
		Mometasone furoate	0	0.1
		Triamcinolone acetonide	C or O	0.5
	IV	Betamethasone valerate	C, F, L, or O	0.1
Medium		Clocortolone pivalate	С	0.1
		Desoximetasone	С	0.05
		Fluocinolone acetonide	C or O	0.025
		Flurandrenolide	C or O	0.05
		Fluticasone propionate	0	0.005
		Mometasone furoate	С	0.1
		Triamcinolone acetonide	C or O	0.1
Lower- medium	V	Hydrocortisone butyrate	C, O, or S	0.1
		Hydrocortisone probutate	С	0.1
		Hydrocortisone valerate	C or O	0.2
		Prednicarbate	С	0.1
	VI	Alclometasone dipropionate	C or O	0.05
Low		Desonide	C, G, F, or O	0.05
		Fluocinolone acetonide	C or S	0.01
Lowest	VII	Dexamethasone	С	0.1
		Hydrocortisone	C, L, O, or S	0.25, 0.5, or 1
		Hydrocortisone acetate	C or O	0.5-1

C = cream; F = foam; G = gel; L = lotion; O = ointment; S = solution; TCS = topical corticosteroid.

REFERENCES

Eichenfield et al 2014, J Am Acad Dermatol 71(1):116-132.

Appendix H Investigator's Global Assessment

The Investigator's Global Assessment is not standardized, so the version provided should be used (Table H1).

Table H1 **IGA**

Score	Disease Severity	Standard IGA Scale	IGA Morphological Descriptors
0	Clear	No inflammatory signs of AD.	No erythema and no elevation (papulation/infiltration).
1	Almost clear	Just perceptible erythema, and just perceptible papulation/infiltration.	Barely perceptible erythema and/or minimal lesion elevation (papulation/infiltration) that is not widespread.
2	Mild disease	Mild erythema and mild papulation/infiltration.	Visible detectable, light pink erythema and very slight elevation (papulation/infiltration).
3	Moderate disease	Moderate erythema and moderate papulation/infiltration.	Dull red, clearly distinguishable erythema and clearly perceptible but not extensive elevation (papulation/infiltration).
4	Severe disease	severe erythema and severe papulation/infiltration.	Deep/dark erythema, marked and extensive elevation (papulation/infiltration).

AD = atopic dermatitis; IGA = Investigator's Global Assessment.

SIGNATURE PAGE

This is a representation of an electronic record that was signed electronically and this page is the manifestation of the electronic signature

Document Name: d9182c00001-csp-amendment-9						
Document Title:	D9182C00001 Clinical Study Protocol Amendment 9					
Document ID:	Doc ID-004360626					
Version Label:	5.0 CURRENT LATEST APPROVED					
Server Date (dd-MMM-yyyy HH:mm 'UTC'Z)	Signed by	Meaning of Signature				
21-Jun-2022 07:01 UTC	[name]	Author Approval				
20-Jun-2022 09:18 UTC	[name]	Content Approval				
20-Jun-2022 07:24 UTC	[name]	Content Approval				

Notes: (1) Document details as stored in ANGEL, an AstraZeneca document management system.

EASI	Eczema Area and Severity Index
EASI 50	50% reduction from baseline in Eczema Area and Severity Index score
EASI 75	75% reduction from baseline in Eczema Area and Severity Index score
EASI 90	90% reduction from baseline in Eczema Area and Severity Index score
ECG	electrocardiogram
eCRF	electronic case report form
EDC	electronic data capture
EDN	Eosinophil Derived Neurotoxin
E _{max}	maximum effect attributable to the drug
GEE	Generalized Estimating Equation
ICH	International Council for Harmonisation
IGA	Investigator's Global Assessment
IL	interleukin
IPD	Important protocol deviation
ITT	intent-to-treat
IXRS	interactive voice/web response system
IV	intravenous
mAb	monoclonal antibody
MCP-Mod	multiple comparison procedure with modelling techniques
MedDRA	Medical Dictionary for Regulatory Activities
MMRM	mixed-effects model for repeated measures
NRS	Numerical Rating Scale
NT-proBNP	N-terminal prohormone of B-type natriuretic peptide
PD	pharmacodynamic(s)
PDP	protocol deviation plan
PGI-S	Patient Global Impression of Severity

Abbreviation or Specialized Term	Definition
PK	pharmacokinetic(s)
POEM	Patient-Oriented Eczema Measure
PT	preferred term
SAE	serious adverse event
SAP	Statistical Analysis Plan
SC	subcutaneous
SCORAD	SCORing Atopic Dermatitis
SD	standard deviation
SNOT	Sino-nasal Outcome Test
SOC	system organ class
TBL	total bilirubin
TCI	topical calcineurin inhibitor
TCS	topical corticosteroid
TEAE	treatment-emergent adverse event
TESAE	treatment-emergent serious adverse event
TS	Translational Science
ULN	upper limit of normal
Q4W	every 4 weeks

1 INTRODUCTION

This document describes the statistical analysis for protocol D9182C00001, a Phase 2 proof-of-concept clinical study which aims to evaluate the efficacy and safety of MEDI3506 in subjects with moderate to severe Atopic Dermatitis (AD).

2 STUDY OVERVIEW

2.1 Study Objectives

2.1.1 Primary Study Objective(s)

The primary objective of the study is to assess the effects of MEDI3506 compared with placebo on AD disease severity, in adult subjects with moderate-to-severe AD.

2.1.2 Secondary Study Objectives

The secondary objectives are:

- To further assess the effects of MEDI3506 compared with placebo on AD disease severity and symptoms, in adult subjects with moderate-to-severe AD
- To assess the safety and tolerability of MEDI3506 compared with placebo, in adult subjects with moderate-to-severe AD
- To evaluate the PK of MEDI3506, in adult subjects with moderate-to-severe AD
- To evaluate the immunogenicity of MEDI3506, in adult subjects with moderate-to-severe AD.

2.1.3 Exploratory Study Objectives

The exploratory objectives are as follows:

- To assess the effects of MEDI3506 compared with placebo on AD disease severity and symptoms over time to Week 24, in adult subjects with moderate-to-severe AD
- To evaluate the effect of MEDI3506 on blood biomarkers that may either predict or reflect an efficacy response in adult subjects with moderate-to-severe AD
- To evaluate the effect of MEDI3506 on skin biomarkers that may either predict or reflect an efficacy response in adult subjects with moderate-to-severe AD

[figure not shown]
- To assess the effect of MEDI3506 compared with placebo on the need for rescue therapy, in adult subjects with moderate-to-severe AD
- To evaluate the effect of MEDI3506 compared with placebo on nasal symptom control, in a subset of adult subjects with moderate-to-severe AD and comorbid chronic inflammatory conditions of the nasal mucosa and/or paranasal sinuses
- To evaluate the effect of MEDI3506 on asthma symptom control compared with placebo, in a subset of adult subjects with moderate-to-severe AD and comorbid asthma.
- To evaluate genetic markers that may predict an efficacy response in adult subjects with moderate-to-severe AD treated with MEDI3506 compared with placebo.

2.2 Study Design

This is a Phase 2 randomized, double-blinded, placebo-controlled, parallel-group, proof-of-concept study to evaluate the efficacy, safety, PK, and immunogenicity of MEDI3506 in adult subjects with moderate-to-severe AD. Approximately 152 subjects will receive [CCI] MEDI3506 SC; or pooled placebo SC; in a 3:1:1:3 ratio overall, [CCI] The randomization ratio will change during the study. The first 72 subjects in the study will be randomized using a 3:3:3:1:2 ratio to receive [CCI] MEDI3506 SC; or placebo [CCI] SC, or placebo [CCI] SC. The remaining subjects will be randomized using a 1:1 ratio to receive [CCI] MEDI3506 SC or placebo [CCI] SC. The randomization will be stratified based on total IgE (< 150 kU/L or ≥ 150 kU/L) at screening.

Subjects will be enrolled in this study for approximately 6.8 months (28 weeks), comprising a screening and TCS/TCI wash out period of up to 4 weeks, a 16-week treatment period, and an 8-week follow-up period (Figure 1). Subjects will not be permitted to use TCSs and TCIs during these periods, except if medically necessary. The final dose of investigational product will be administered at Visit 9 (Week 12) and the primary endpoint assessment will occur at Visit 10 (Week 16).

Figure 1: Study Flow Diagram

2.3 Treatment Assignment, Blinding and Analysis Datasets

At Visit 3 (Day 1), eligible subjects will be randomized to receive SC investigational product CCI, as follows:

- MEDI3506 CCI (58 subjects),
- MEDI3506 CCI (18 subjects),
- MEDI3506 CCI (18 subjects),
- Placebo CCI (6 subjects), or
- Placebo CCI (52 subjects).

The randomization will be stratified based on total IgE (< 150 kU/L or ≥ 150 kU/L) at screening. An IXRS will be used for randomization to a treatment group and assignment of blinded investigational product kit numbers. A subject is considered randomized into the study when the investigator notifies the IXRS that the subject meets eligibility criteria and the IXRS provides the assignment of blinded investigational product kit numbers for the subject. Neither the subject nor any of the investigator or sponsor staff who are involved in the treatment or clinical evaluation of the subjects will be aware of the treatment received.

MEDI3506 could reduce eosinophil counts in blood over time. As a precaution, eosinophil, basophil, and monocyte data from the hematology laboratory tests will not be communicated to blinded sponsor or site personnel during the treatment and follow-up periods.

The primary analysis will occur once all subjects have either completed the Visit 10 (Week 16) assessments or have withdrawn from the study. All the available data at the time of primary analysis will be included. The sponsor staff will be unblinded following database lock for the primary analysis. Investigators and site staff will not be made aware of unblinded treatment assignments for individual subjects who are in the follow-up period until these subjects have completed the study.

The final analysis will occur when all subjects have completed the follow up period at Visit 12 (Week 24) or have withdrawn from the study.

2.3.1 Analysis Datasets

The primary analysis datasets contain all data (efficacy, safety, ADA, and PK) from all randomized subjects through Visit 10 (Week 16), and all available safety data as of the data cut-off date.

The final analysis datasets contain all data collected in this study, including data in the primary datasets and data from the subjects who were ongoing in the study at the time when the primary datasets were locked.

2.4 Sample Size

A sample size of 144 subjects in an overall 3:1:1:3 ratio of MEDI3506 CCI : MEDI3506 CCI : MEDI3506 CCI : pooled placebo will provide at least 90% power to detect a statistically significant difference in the percent change from baseline to Week 16 in EASI score between the highest dose of MEDI3506 and pooled placebo in a responder subgroup, assuming a 35% point difference between placebo and MEDI3506 at the highest dose, based on a SD of 40% points, a two-sided 10% alpha level and 50% of subjects in the responder subgroup. Based on identical assumptions, the sample size provides > 99% power to detect a statistically significant dose response in percent change from baseline to Week 16 in EASI score in all-comers.

The calculations for dose-response assume that percent change from baseline to Week 16 in EASI score will increase monotonically with the administration of higher MEDI3506 doses. The power was calculated using a multiple comparison procedure with modelling techniques (MCP-Mod) (Bretz et al, 2005) with 4 candidate models for the dose response (linear, maximum effect attributable to the drug [E_{max}], and 2 Hill- E_{max} models). Randomization will be stratified by total IgE (< 150 kU/L or \geq 150 kU/L) at screening. The sample size calculations were performed using the R statistical computing software.

To allow for the possibility that \leq 5% of the subjects per treatment group (for MEDI3506 CCI and placebo) may be ineligible for the ITT population, the total sample size will comprise approximately 152 subjects (58 MEDI3506 CCI, 18 for MEDI3506 CCI, 18 for MEDI3506 CCI, and 58 for pooled placebo) randomized approximately to 3:1:1:3 ratio overall to the treatment groups.

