4.8.2 Sample Size

A sample size of 144 subjects in an overall 3:1:1:3 ratio of MEDI3506 CCI :MEDI3506 :MEDI3506 :MEDI3506 :pooled placebo, will provide at least 90% power to detect a statistically significant difference in the percent change from baseline to Week 16 in EASI score between the highest dose of MEDI3506 and pooled placebo in a responder subgroup, assuming a 35% point difference between placebo and MEDI3506 at the highest dose, based on a SD of 40% points, a two-sided 10% alpha level, and 50% of subjects in the responder subgroup. Based on identical assumptions, the sample size provides > 99% power to detect a statistically significant dose response in percent change from baseline to Week 16 in EASI score in all-comers.

The calculations for dose response assume that percent change from baseline to Week 16 in EASI score will increase monotonically with the administration of higher MEDI3506 doses. The power was calculated using a multiple comparison procedure with modelling techniques (MCP-Mod) (Bretz et al, 2005) with 4 candidate models for the dose response (linear, maximum effect attributable to the drug [E_{max}], and 2 Hill- E_{max} models). Randomization will be stratified by total IgE (< 150 kU/L or \geq 150 kU/L) at screening.

To allow for the possibility that $\leq 5\%$ of the subjects per treatment group may be ineligible for the ITT population, the total sample size will comprise approximately 152 subjects (58 for MEDI3506 CCI , 18 for MEDI3506 CCI , and 58 for pooled placebo) randomized approximately to 3:1:1:3 ratio overall to the treatment groups.

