The estimand of primary interest is the difference in mean percent change from baseline to Week 16 in EASI score between MEDI3506 and placebo in the ITT population. Data that are collected after withdrawal from the study or the use of rescue therapy will be treated as missing and excluded from the analysis. Data collected from subjects who discontinue the investigational product and did not use any rescue therapy afterwards will be included in the analysis. From the final model obtained from the MCP-Mod dose response analysis, the adjusted difference in mean percent change from baseline in EASI score between the placebo group and each MEDI3506 group at Week 16 will be estimated along with the 90% confidence interval (CI) and two-sided p-value. In addition, an estimate of the adjusted difference in mean percent change from baseline in EASI at each visit for each treatment group compared to placebo arm will be summarized together with a two-sided 90% CI, and p-value.

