3.4.1.5 Subgroup Analyses

The consistency of the overall treatment effect on the primary endpoint will be assessed in subgroups of subjects. A MMRM, as described in Section 3.4.1.3, including data from up to Week 16, will be used for each subgroup. The analyses will be performed for subgroups, as follows:

- Total serum IgE level at baseline (< 150 kU/L vs ≥ 150 kU/L).
- Baseline IGA score (3 vs 4).
- Baseline EASI (≤ 25 points vs > 25 points).
- *S aureus* in lesional skin at baseline ($<$ median vs \geq median) (at final analysis only).
- *S aureus* in non-lesional skin at baseline ($<$ median vs \geq median) (at final analysis only).
- Age (18 to 35 years of age vs 36 to 75 years of age).
- Age at onset of AD (< 18 years of age vs ≥ 18 years of age).
- Parent having a history of AD (presence vs absence).

- Sex (male vs female).
- Race (White vs non-White).
- Region (North America vs Europe/Australia).
- Blood eosinophil count at baseline (< 300 cells/ μL vs ≥ 300 cells/ μL).
- Aeroallergens (presence vs absence).
- Food allergies (presence vs absence).
- Contact allergies (presence vs absence).
- Asthma comorbidity (presence vs absence).

The MMRM will be fitted separately to each subgroup. The analysis for each subgroup will be performed if the subgroup has at least 20% of subjects in the ITT population.

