Appendix 1 Determination of dose-response profile using MCP-Mod

To determine dose-response profile using MCP-Mod, the candidate models first need to be defined. For this study, four candidate models will be used for the MCP-Mod models and these are: Linear, E_{max} and 2 Hill- E_{max} models. The description of the function of each model and the parameters are specified below:

- Linear Model: $f(d, \theta) = E_0 + \delta d$
- E_{max} Model: $f(d, \theta) = E_0 + E_{max} \frac{d}{ED_{50} + d}$
- Hill- E_{max} Model: $f(d, \theta) = E_0 + E_{max} \frac{d^h}{ED_{50}^h + d^h}$

where d denotes the dose parameter; E_0 is the placebo effect; δ is the slope parameter for the linear model; E_{max} is the asymptotic maximum effect; ED_{50} is the dose giving half of the asymptotic maximum effect; h is the hill parameter which determines the steepness of the model as the ED_{50} .

For the percent change from baseline to Week 16 in EASI endpoint, the models are defined as follows:

$$fmodels = Mods(linear = NULL, emax = 150, sigEmax = rbind(c(150,3), c(450,3)), \\ doses = c(\text{CCI}), placEff=0, maxEff=35, direction = c("decreasing")).$$

where $maxEff$ is the maximum effect over placebo.

For the percentage of subjects achieving IGA response at Week 16 endpoint, the models are defined as follows on the logit scale:

$$fmodels = Mods(linear = NULL, emax = 150, sigEmax = rbind(c(150,3), c(450,3)), \\ doses = c(\text{CCI}), placEff=logit(10), maxEff=logit(30)-logit(10), \\ direction=c("increasing"))$$

where $logit(x)$ is $\log(x/(1-x))$.

For the percentage of subjects achieving EASI 75 response at Week 16 endpoint, the models are defined as follows:

$$fmodels = Mods(linear = NULL, emax = 150, sigEmax = rbind(c(150,3), c(450,3)), \\ doses = c(\text{CCI}), placEff=logit(15), maxEff=logit(35)-logit(15), \\ direction=c("increasing")).$$

Once the models are defined, then the MCP-Mod analysis is performed. For the percent change from baseline to Week 16 in EASI endpoint, the MCP-Mod analysis is performed as follows:

$$MM = MCPMod(dose = doses, EstEffects, S = vCov, models = fmodels, type = "general", placAdj = FALSE, Delta = 35, alpha = 0.1, alternative = c("two.sided"))$$

where

- “*doses*” denotes the vector of doses,
- “*EstEffects*” denotes the vector of estimated coefficient obtained from the MMRM,
- “*vCov*” denotes the estimated variance-covariance matrix,
- “*fmodels*” is the specified candidate models,

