- “*type*=“general” ” indicates that the estimates and their covariance matrix are specified,
- “*placAdj* =FALSE” indicates that the estimated specified are not placebo-adjusted,
- “*Delta*” is the target effect size over placebo,
- “*alpha*” is the significance level for the multiple contrasts.

For the percentage of subjects achieving IGA response at Week 16 endpoint, the MCP-Mod analysis is performed as follows:

$$MM = MCPMod(dose = doses, EstEffects, S = vCov, models = fmodels, type = "general", placAdj = FALSE, Delta = \logit(30) - \logit(10), alpha = 0.1, alternative = c("two.sided"))$$

where

- “*EstEffects*” denotes the vector of estimated coefficient obtained from the fitted logistic regression model,
- “*vCov*” denotes the estimated variance-covariance matrix.
- All the other parameters are the same as those described above for the EASI endpoint.

For the percentage of subjects achieving EASI 75 response at Week 16 endpoint, the MCP-Mod analysis is performed as follows:

$$MM = MCPMod(dose = doses, EstEffects, S = vCov, models = fmodels, type = "general", \\ placAdj = FALSE, Delta = \text{logit}(35) - \text{logit}(15), alpha = 0.1, \\ alternative = c("two.sided"))$$

where the parameters are the same as those described for the IGA endpoint.

The IGA and EASI 75 results are then back transformed from the logit scale to percentages.

SIGNATURE PAGE

This is a representation of an electronic record that was signed electronically and this page is the manifestation of the electronic signature

Document Name: d9182c00001-sap-v3		
Document Title:	Statistical Analysis Plan Version 3	
Document ID:	Doc ID-004755752	
Version Label:	1.0 CURRENT LATEST APPROVED	
Server Date (dd-MMM-yyyy HH:mm 'UTC'Z)	Signed by	Meaning of Signature
11-Jul-2022 09:56 UTC	[name]	Management Approval

Notes: (1) Document details as stored in ANGEL, an AstraZeneca document management system.

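### Does the > 99% all-comers power rest on an effect that the plan does not state outside the responder half?

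*SAP*

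**What the plan says.** SAP 2.4 gives two power figures for 144 subjects in a 3:1:1:3 ratio. The first is at least 90% for the highest dose against pooled placebo in a responder subgroup. It takes a 35-point difference in percent change in EASI, an SD of 40 points, and "a two-sided 10% alpha level and 50% of subjects in the responder subgroup". The second reads: "Based on identical assumptions, the sample size provides > 99% power to detect a statistically significant dose response in percent change", and refers to all-comers. Protocol 4.8.2 carries both sentences with the same inputs ("a two-sided 10% alpha level, and 50% of subjects in the responder subgroup").

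SAP Appendix 1 specifies the candidate models for the EASI endpoint with "placEff=0, maxEff=35" and the analysis call with "Delta = 35, alpha = 0.1". It explains that Delta "is the target effect size over placebo".

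The primary analysis uses the ITT set, which is all treated subjects. SAP 3.4.1.3 says: "The estimand of primary interest is the difference in mean percent change from baseline to Week 16 in EASI score between MEDI3506 and placebo". SAP 3.4.1.5 lists subgroup factors for a different purpose: "The consistency of the overall treatment effect on the primary endpoint will be assessed in subgroups of subjects". None is labelled as the responder subgroup. SAP 5 describes a post hoc exploratory search for patients who benefit more. It will use a biomarker list supplied before the primary database lock and its own analysis plan, and will be reported outside the CSR.

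**The concern.** The first sentence ties the 35 points to a responder subgroup holding half the subjects. The second claims > 99% for everyone on the same assumptions. If the 35 points is what responders gain, and the other half gains less, the all-comers mean is below 35 and the assumptions are not the same. The effect in the other half is never given. SAP 5 speaks of patients with enhanced benefit, which suggests the halves are expected to differ.

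If that were right, the headline power for the ITT primary analysis would be too favourable. A reader could not tell how far it falls under partial response. The 90% figure would describe a comparison in a subgroup that the plan does not define in advance.

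**Working it through.** **Inputs.** 144 subjects at 3:1:1:3 give 54 / 18 / 18 / 54 (SAP 2.4). Half of 54 is 27 per arm for the subgroup. The difference is 35, the SD 40, alpha two-sided 0.10 (SAP 2.4). The candidate shapes are linear, Emax with ED50 150, and Hill-Emax with (150, 3) and (450, 3) (SAP Appendix 1). The top dose is 600 mg (Protocol 4.6.1). The two lower doses are redacted, so ten pairs were assumed: 30/150, 60/300, 75/300, 100/300, 150/300, 50/150, 200/400, 150/450, 300/450 and 10/50.

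**Formula, pairwise.** Power is the probability that a noncentral t variable with 2n − 2 degrees of freedom and noncentrality λ = δ / (40 × √(2/n)) exceeds the two-sided 10% critical value in absolute size.

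**1. The subgroup figure.** For n = 27, the standard error is 40 × √(2/27) = 10.89, and λ = 35 / 10.89 = 3.21. Power is 93.7%. The stated minimum of 90% holds.

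**2. The all-comers figure, taking 35 points as the all-comers mean.** For n = 54, the standard error is 40 × √(2/54) = 7.70, and λ = 35 / 7.70 = 4.55. Pairwise power is 99.8%. MCP-Mod was simulated with optimal contrasts for the four shapes and a multiplicity-adjusted two-sided 10% critical value. Each shape was taken as the truth in turn, with 200,000 replicates. Power was 99.8% to 100% over all shapes and dose pairs. The stated > 99% holds.

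**3. What > 99% requires.** Solving for 99% gives an all-comers mean of 30.8 points pairwise and 27.7 to 30.8 by MCP-Mod. If responders gain 35, the other half must gain 2 × 27.7 − 35 = 20.4 to 2 × 30.8 − 35 = 26.6 points. The value of 35 in Appendix 1 is above this threshold.

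**4. Whether the two figures force equal halves.** They do not, because both are lower bounds.

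| Responders | Other half | All-comers mean | Subgroup power | All-comers power (pairwise) |
|---|---|---|---|---|
| 35 | 35 | 35 | 93.7% | 99.8% |
| 35 | 27 | 31 | 93.7% | 99.1% |
| 45 | 25 | 35 | 99.3% | 99.8% |

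Pairwise, any responder effect of at least about 32.3 points with an all-comers mean of at least about 30.8 satisfies both.

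**5. Where the all-comers figure fails.** Responders are held at 35 points. The effect in the other half is an assumption with no source in the documents.

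| Other half | All-comers mean | Pairwise | MCP-Mod |
|---|---|---|---|
| 17.5 | 26.25 | 96% | 96–98% |
| 10 | 22.5 | 90% | 89–94% |
| 0 | 17.5 | 73% | 73–81% |

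**The case for a change.** The strongest case is that partial response is a live scenario for this trial. Protocol 1.2 reports that another anti-IL-33 antibody missed its EASI primary endpoint in a Phase 2b study. The amendment log says that Amendment 3 enlarged this study in response, and the SAP version history ties both the revised sizing section and the post hoc responder section to that amendment. A reader may therefore want all-comers power when only part of the population responds well, and the text does not supply it. If everyone gains 35 points, calling half of them responders does no work beyond setting a subgroup size. Appendix 1 also defines models for the analysis, and is not itself a record of the power calculation.

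Part of this stands. The all-comers mean is not written out in either sizing section, and no responder subgroup is fixed in advance. The rest does not. Neither sizing section says that the drug works mainly in one half. The 35 points is described as the difference at the highest dose, and the 50% can be read as setting only the size of the subgroup. Enhanced benefit in some patients, the language of SAP 5, does not mean little benefit in others. The lower powers come from effects of 0, 10 or 17.5 points that the documents do not contain. The natural rewording would state 35 points for all-comers, keep > 99%, and leave 35 points in both sentences, so it would not remove the pairing objected to. A disclaimer on the 90% figure would largely repeat SAP 5.

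**Conclusion.** No change is called for. Both figures follow from the stated inputs (93.7% against at least 90%, 99.8% against > 99%), and the documents do not show a power that the design fails to deliver. What remains is missing detail that an analyst fills from Appendix 1: the all-comers difference is taken as 35 points.

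This rests on reading the 35 points as applying to all subjects, or on any pair of effects that keeps the all-comers mean at about 28 to 31 points or more. The lower end of that range depends on assumed values for the redacted doses; the pairwise 30.8 does not. If the effect outside the responder half were below roughly 20 to 27 points, power would fall short of 99%, to 73% in the extreme case of no effect there. That is a caveat on how to read the figure, and not an error in it.

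The 90% figure is best read as illustrative, since the subgroup will be identified post hoc and outside the CSR, as SAP 5 says. The primary inference is in the ITT population and makes no use of the subgroup. Sample size, test, alpha, estimand and conclusions are the same with or without extra wording.
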